- 5. English speaking and able to give informed consent
- 6. Willing and able to complete all study questionnaires
- 7. Ambulatory

Exclusion Criteria

- 1. Prior sacrospinous ligament fixation procedure.
- 2. Any serious disease or chronic condition that could interfere with the study compliance
- 3. Inability to give informed consent
- 4. Pregnancy or planning pregnancy prior to the 6 week postoperative visit
- 5. Prior pelvic radiation
- 6. Incarcerated

- 7. Prior augmented (synthetic mesh, autologous graft, xenograft, allograft) prolapse repair
- 8. History of significant buttock or leg pain in the past 3 months
- 9. History of fibromyalgia, polymyositis, dermatomyositis, systemic lupus erythematosus, or other auto-immune myalgic conditions
- 10. Current regular narcotic drug therapy for any chronic pain condition
- 11. History of loss of motor or sensory function of the lower extremities
- 12. History of sacral decubitus ulcers
- 13. Planned concomitant levatorplasty; anal sphincteroplasty, anal fissurectomy, rectopexy, or hemorrhoidectomy

STUDY POPULATION, RECRUITMENT AND SCREENING

Study population participants will consist of women who are scheduled to undergo native tissue POP repair using apical support to the sacrospinous ligament. Women scheduled to undergo sacrospinous hysteropexy and sacrospinous suspension of the vaginal vault will be recruited at Wake Forest Baptist Medical Center.

Participants must have vaginal bulge symptoms defined by positive responses to a validated instrument, the Pelvic Floor Distress Inventory (PFDI)^{14,15}, Stage II or greater POP in any vaginal compartment as determined by the Pelvic Organ Prolapse Quantification (POPQ) system,¹⁶ a validated tool designed to assess the degree of vaginal prolapse, and an apical prolapse contribution to the patient's overall pelvic organ prolapse as deemed by the examining physician. An apical prolapse contribution is detected by either the descent of the "C" component of the POP-Q system or as the demonstration of at least partial correction of an anterior or posterior prolapse via manipulated suspension of the apex during on pelvic examination.

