A computer-generated random allocation using a randomly permutated block design (10-patients per block) will be utilized. Randomization will be performed at the start of the study with study group assignments placed in sealed nontransparent envelopes. The envelopes will be numbered in order. The next envelope in numerical order will be brought to the operating room where it will be opened by a participating surgeon and another operating room staff member. Both personnel will sign the envelope to validate that proper envelope opening and interpretation were performed. The envelopes will then be collected for record keeping. This procedure will help to minimize surgeon bias as it is impossible for surgeons to be masked to the randomization. Participants and research staff will be masked during the study as much as possible, however there will be a description of the type of sacrospinous ligament fixation device used within the body of the operative note for each patient that research staff could gain access to. Intraoperative data, including any adverse event that may unmask the study coordinators, will be reported by the surgeon directly to the study administrators.

STUDY INTERVENTION

The primary intervention is sacrospinous fixation utilizing either the Anchorsure® system or the Capio[™] Slim device. Concomitant anterior and/or posterior colporrhaphy (plication of fibromuscular vaginal tissue), enterocele repairs, transvaginal hysterectomy, bilateral salpingo-oophorectomy, perineoplasty, midurethral sling procedures, or other procedures not involving the pelvis, anus, buttock, or lower extremities may be performed. Prolapse procedures will be recorded but not controlled by study protocol. Participating surgeons are all extensively experienced in sacrospinous ligament fixation. Any use of allograft, xenograft, or synthetic graft material for POP repair will not be permitted.

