This study is a head to head two sample comparative study. The null hypothesis is that there is no difference in the prevalence of immediate postoperative new buttock or posterior thigh pain with the use of the Anchorsure® System compared to the Capio[™] Slim device for sacrospinous ligament fixation. In prior published study by Ferrando et al the mean postoperative day 1 buttock or posterior thigh pain had a greater standard deviation (2.7-2.9) compared to week

1 and week 6 data. Therefore for our power calculation used an expected standard deviation of 2.9 to provide confidence in our power of assessing the difference in pain scores across all three timepoints.²² A decrease in in-hospital postoperative buttock or posterior thigh pain prevalence of 2.5 on a 10-point scale was chosen as clinically significant and is consistent with published data.^{22,18,17} Using a standard deviation of 2.9 and a difference in pain scores of 2.5 setting the level of significance, 21 patients are required in each group to provide a power of at least 80% to reject the null hypothesis (H0) that the Anchorsure® System does not lead to significantly less postoperative buttock and posterior thigh pain than does the Capio[™] Slim Device in favor of the alternate hypothesis that the Anchorsure® System leads to significantly less postoperative pain than the Capio[™] Slim Device using a two-sample normal approximation test of means with a two-sided 5% significance level. Assuming a 15% loss to follow-up or drop-out rate for the duration of the study, the total enrollment goal is 48 patients (24 in each group). The null hypothesis will be declared rejected if the mean of immediate postoperative buttock and posterior thigh pain with use of the Anchorsure® device is less from the mean with the use of the Capio[™] Slim device with a p-value of 0.05 or less. The power calculations and their adjustment from the original study goal of 60 recruited patients (using 90% power and a standard deviation of 3) were confirmed with the Wake Forest Baptist Hospital CTSI Biostatistics Department.

Form / Intervention	Preop Clinic	Intra- operatively	Day 1	Week 1	Week 6
Informed Consent	Х				
Study Inclusion Form	Х				
Preop Baseline Data Form with					
Charlson Comorbidity Index and	Х				
POP-Q					
PFDI-20 and PFIQ-7 Forms	Х				Х
NRS Pain Questionnaires	Х		Х	Х	Х
Oral Opioid Use Questionnaire				Х	
Randomization		Х			
Adverse events		Х	Х	Х	Х
Surgeon Questionnaire		Х			

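### A constant, disclosed block of 10 in one single-centre sequence leaves some allocations guessable by unmasked surgeons who pool the tally; larger undisclosed blocks summing to 48 would reduce this cheaply

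*Combined protocol and SAP*

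**What the plan says.** The Randomization and Masking section fixes the scheme: "A computer-generated random allocation using a randomly permutated block design (10-patients per block) will be utilized". It gives no variation in block size and no strata. The list is made in advance: "Randomization will be performed at the start of the study with study group assignments placed in sealed nontransparent envelopes". The envelopes are numbered and used in order: "The next envelope in numerical order will be brought to the operating room where it will be opened by a participating surgeon", together with a second staff member. On checking, the section says: "Both personnel will sign the envelope to validate that proper envelope opening and interpretation were performed". It also accepts that "it is impossible for surgeons to be masked to the randomization".

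Under Study Population, Recruitment and Screening, women "will be recruited at Wake Forest Baptist Medical Center", so there is one site. Entry depends in part on judgement, including "an apical prolapse contribution to the patient's overall pelvic organ prolapse as deemed by the examining physician".

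The Calendar of Events places consent in the preoperative clinic and randomization in the operating room. The Power Calculation section says "the total enrollment goal is 48 patients (24 in each group"), reduced from an original goal of 60.

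The document does not say who prepares or holds the list, whether surgeons may see the block size or a running tally, how many surgeons share the list, or what is recorded when a consented patient is rescheduled or not randomized.

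**The concern.** Opaque envelopes hide the card inside. They do not hide what earlier cards imply about the next one. Once one arm has used its share of a block, the rest of that block is known. Here the block length is constant and is printed in the protocol, there is only one sequence to follow, and the surgeons learn each allocation as they use it. The device is also described in each operative note, so a colleague's past allocations could be traced.

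Envelope order follows operating order. Someone who expects a given device next could therefore influence who is booked into that slot, or the order of cases on a list. The primary outcome is self-reported pain, compared by an unadjusted t-test. Concomitant prolapse procedures are recorded but not controlled. If patients expected to have more pain were steered towards one device, the planned comparison would carry that difference.

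**Working it through.** **Inputs.** From the protocol: block of 10, one centre, one sequence, 48 patients planned as 24 per group, target difference 2.5 NRS points, SD 2.9. Assumed: each block holds 5 of each device (the section does not give the ratio; 24 per group implies it), and an observer who knows the block size and all past allocations.

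**The plan's own figure.** The plan gives no figure for predictability. Its sample size is in line with its inputs: 2 × [2.9 × (1.960 + 0.842) / 2.5]² = 21.1 per group, against the stated 21. The target of 48 is taken as it stands.

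**Allocations known with certainty.** After k allocations in a block (k ≥ 5), the next is certain if one arm has used all five places. The probability is 2 × C(5, k−5) / C(10, k):
- 6th: 2/252 = 0.8%
- 7th: 10/210 = 4.8%
- 8th: 20/120 = 16.7%
- 9th: 20/45 = 44.4%
- 10th: 100%

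The sum is 1.67 per block; the first five are never certain. Forty-eight patients make four full blocks plus eight: 4 × 1.667 + (0.008 + 0.048 + 0.167) = 6.9.

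**Correct guesses.** The best guess is always the arm that is behind. In a block of 2h the expected number correct is h + (4^h / C(2h, h) − 1)/2. For h = 5 this is 5 + (1024/252 − 1)/2 = 6.53 of 10. The 9th and 10th positions contribute 0.722 and 1.000, so the first eight contribute 4.81. Over 48 patients: 4 × 6.532 + 4.81 = 30.9, or 64.5%, against 50% by chance.

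**Bias if every guess is used.** Suppose the surgeon assigns patients whose expected pain differs by s points according to the guess, with accuracy g. The arms then differ by [g − (1 − g)] × s = (2g − 1)s. With g = 0.6445 this is 0.289s: 0.14 points for s = 0.5, 0.29 for s = 1 and 0.58 for s = 2. The values of s are assumptions.

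**Alternatives summing to 48.** The same guess formula applies; certain allocations per block of 2h are 2h/(h + 1).

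| Scheme | Correct guesses of 48 | Certain, if sizes and order are known |
|---|---|---|
| Blocks of 10 (plan) | 30.9 (64.5%) | 6.9 |
| Six 4s and four 6s | 6 × 2.833 + 4 × 4.100 = 33.4 (69.6%) | 6 × 1.333 + 4 × 1.5 = 14.0 |
| 12, 16 and 20 | 7.72 + 10.05 + 12.34 = 30.1 (62.7%) | 1.71 + 1.78 + 1.82 = 5.3 |

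Guessing the arm that is behind needs only the running tally, so hiding the sizes leaves the middle column unchanged. Hiding them acts on the last column.

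**Final split.** Stopping at 48 falls eight envelopes into the fifth block. P(4/4) = C(5,4)² / C(10,8) = 25/45 = 55.6%; otherwise (44.4%) the split is 25/23. The information lost is 1 − (25 × 23/48)/12 = 0.2%.

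**The case against.** The strongest reply is that these figures describe an observer the documents do not show to exist. The protocol refers to several surgeons and recruits through Urology and Gynecology. A surgeon sees only his or her own cases unless results are pooled, and opened envelopes are collected for record keeping. Even the fully informed observer is certain of only about 1 allocation in 7 (6.9 of 48). Among constant sizes, 10 is less predictable than 4, 6 or 8, where the certain share of a complete block is 33.3%, 25.0% and 20.0%, against 16.7%. All of this stands, and it limits the size of the point.

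A reader might also infer that opening envelopes in theatre is the weakness. It is not. It comes after consent and baseline assessment, uses sealed opaque numbered envelopes, and is witnessed and signed by two people. To use a guess, a surgeon would have to foresee the list position at booking or reorder cases. Surgeons learn past allocations in any device trial where they cannot be masked.

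Nor would steering be undetectable. Baseline pelvic pain, POP-Q, medical history, surgical approach and concomitant procedures are recorded, so comparing the arms on these could partly reveal it, though weakly with 48 patients.

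What remains is that the block size is constant and printed, and that nothing in the document restricts access to the size or the tally.

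**Conclusion.** The weakness is real, minor to moderate, and cheap to reduce. The 6.9 certain allocations and 64.5% correct guesses are upper limits. They assume 5:5 blocks, knowledge of the block size and a complete tally shared across surgeons. The bias of 0.14 to 0.58 NRS points further assumes that every guess is acted on and that steered patients differ by 0.5 to 2 points in expected pain. Partial use of the guesses gives less, and the whole range is well below the 2.5-point target.

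A reader might go further and conclude that surgeons can predict allocations in general, or that selection by device will occur. The documents support neither: most allocations stay uncertain even in the worst case, and no sharing of tallies is described.

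The uneven final split is a side point. It shows that blocks of 10 fitted the original 60 but not 48; its effect on power is negligible.

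**What to change.** In Randomization and Masking, replace the stated block of 10 with permuted blocks of varying size in random order. State that the CTSI Biostatistics group prepares the list and holds the sizes, and keep the sizes out of the protocol and any other document that surgeons see. Choose larger blocks that sum to 48, such as 12, 16 and 20, and not 4s and 6s. If the sizes leak, 12, 16 and 20 still give 62.7% correct guesses and 5.3 certain allocations. If they stay hidden, certainty largely disappears, except at the very end of a list known to close at 24/24. The fall in the guess rate itself is small (64.5% to 62.7%); the main gain is the loss of certainty.

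It would also help to log every consented patient who is not randomized and every change of case order.

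If enrolment has begun, apply the change to the unopened envelopes, sized to the remaining total. An exact 24/24 split then follows only if the switch is made when the arms are level.

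The cost is a short protocol amendment, a regenerated list and re-stuffed envelopes, with no extra patients. The trade-off is a possibly larger imbalance if the trial stops mid-block: up to 10 patients within a block of 20, against 5 within a block of 10.

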Access to the retroperitoneal space will be accomplished either via a circumferential pericervical, an anterior, or a posterior. The method of surgical approach will be recorded. Sharp and blunt dissection will be performed to gain access to the sacrospinous ligament(s). Surgeon discretion will determine if unilateral or bilateral fixation is performed for vaginal vault suspension but only unilateral sacrospinous ligament suspension will be permitted for hysteropexy. Surgeon discretion will determine the type and number of sutures or anchors to be placed through the sacrospinous ligament and this data will be recorded. All sutures and anchors placed into the sacrospinous ligament will be placed at least 2cm medial to the ischial spine. Suture(s) will be placed through any anchors with the choice of suture to be determined by the surgeon as this is not anticipated to interfere with any results. The suture(s) placed through anchors or the sacrospinous ligament directly will then be attached to the cervix and/or vaginal apex. Sacrospinous sutures will be tied down once all mid-vaginal repairs are completed. Transvaginal hysterectomy, bilateral salpingectomy, bilateral oophorectomy, and enterocele repair procedures will be performed prior to sacrospinous ligament fixation.

POST-INTERVENTION ASSESSMENTS

The primary study endpoints will be assessed on postoperative day 1, postoperative week 1, and postoperative week 6 via a NRS. Day 1 questionnaires will be given during morning rounds. 1 week following their procedure, patient's will be called at home to remind them to fill out the week 1 questionnaire that would have been given to them during their hospital stay. This questionnaire will be accompanied with a pre-paid and pre-addressed envelope for the patient to use or, if desired, they can bring the completed week 1 questionnaire to their week 6 follow up appointment. All patients will return to the clinic for 1-week and 6-week post-surgery follow up appointments and will fill out an NRS pain assessment (1-week and 6-week), opioid use questionnaire (1-week), PFDI questionnaire (6-week), physical examination including POP-Q (6-week), and review of any postoperative complications (1-week,6-week).

Clinical outcomes

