This trial has a **primary** outcome of level of postoperative buttock or posterior thigh pain on postoperative day 1, week1, and 6 weeks as measured using the NRS. An independent t-test will be used to compare the means of the NRS scores from the two groups. The NRS is one of the most common validated pain questionnaire modalities.^{17,18,19,20,21} A clinically significant difference will be considered 2.5 on the 10-point NRS based on a prior paper assessing buttock pain from sacrospinous ligament fixation²² and with published studies assessing clinically meaningful decreases in acute pain.^{18,17} The patient's will be given copies of the NRS questionnaire which will be collected in person on postoperative day 1, week 1, and 6 weeks postoperatively.

Secondary outcome measures will assess the degree to which the study intervention influences surgeon satisfaction, surgical efficiency, adverse events intra- and postoperatively, surgical success, symptomatic success, and the level of postoperative general pelvic pain. Surgeon satisfaction will be assessed via a 5-point rating scale (very dissatisfied, somewhat dissatisfied, neutral, satisfied, very satisfied) and treated as categorical values. Surgical efficiency will be assessed as continuous data measured as a means in minutes. Adverse events will be evaluated as dichotomous data. All adverse events will be reported by the Dindo classification system. Short-term objective surgical success will be assessed by a postoperative exam at 6 weeks and descent of the vaginal apex beyond TVL/2 will be considered surgical failure. Symptomatic success will be assessed by the PDFI-20 guestionnaires to be given at 6-weeks post-operation and compared to preoperative values. The patient's will also be queried about their general pelvic pain on the same questionnaires used to assess buttock and posterior thigh pain. Oral opioid use following hospitalization until postoperation day 6 will be recorded via opioid use questions on the 1 week postoperation guestionnaire. The opioid dose will be converted into morphine equivalents for data analysis. Statistical analysis will be done in collaboration with the Wake Forest Baptist Hospital CTSI Biostatistics Department. Independent t-tests will be used for all continuous data, except for the PFDI and PFIQ data that will use paired t-tests as the two samples are dependent. Chi-square tests will be used for all dichotomous and categorical data.

POWER CALCULATION:

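### Planned procedure (hysteropexy or vault suspension) is known before allocation and linked to the pain and device-time outcomes, but is neither stratified nor adjusted for; one prespecified covariate would recover some precision

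*Combined protocol and SAP*

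**What the plan says.** All references are to the combined protocol and SAP.

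- **Eligibility.** Subject Selection admits hysteropexy and post-hysterectomy suspension as part of the surgical plan. Study Population, Recruitment and Screening describes women already scheduled for one or the other.
- **Allocation.** Randomization and Masking specifies permuted blocks of 10 and names no stratification factor. The envelope is opened in the operating room, and the surgeon cannot be masked.
- **Sides.** Study Intervention says that "only unilateral sacrospinous ligament suspension will be permitted for hysteropexy". For vault suspension, one or two sides is left to the surgeon, as is the number of sutures or anchors.
- **Control of procedures.** The same section says "Prolapse procedures will be recorded but not controlled by study protocol". The sentence comes shortly after the list of concomitant operations.
- **Outcomes.** Specific Aim 1 defines the primary outcome as NRS pain on the side or sides of fixation. Specific Aim 2 times the device until every sacrospinous suture is in place.
- **Analysis.** Clinical outcomes states: "An independent t-test will be used to compare the means of the NRS scores from the two groups". Other between-arm continuous data, including device minutes, are also compared by independent t-test. No covariate, subgroup or sensitivity analysis by procedure is described.

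**The concern.** A woman scheduled for hysteropexy can have only one side fixed; a woman scheduled for vault suspension may have two. The protocol's own rules therefore connect a variable known before allocation with the site of the pain being scored and with the amount of work being timed.

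If procedure type does affect pain, two things follow in a trial of 48. A chance imbalance between arms moves the observed difference in that particular trial, and the unadjusted analysis has no planned way to account for it. The variation due to procedure also stays in the error term and costs power. If a covariate is added only after an imbalance is seen, it will look like a choice made with the data in hand.

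**Working it through.** **1. The plan's own sample size.** Power Calculation gives the inputs: "Using a standard deviation of 2.9 and a difference in pain scores of 2.5", and a "two-sample normal approximation test of means with a two-sided 5% significance level".

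- n per arm = 2 × [2.9 × (1.960 + 0.842) / 2.5]² = 21.12. The plan's 21 is reproduced to within rounding; strictly, 21.12 rounds up to 22.
- Power at 21 per arm is 79.8% by the normal approximation and 77.8% by the t-test that will be used.
- For drop-out, 21 × 1.15 = 24.15, which gives the stated 24 per arm and 48 in total.

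**2. How often the arms differ in procedure.** The hysteropexy share is not in the documents, so a range is assumed. With 24 per arm and independent binomial counts:

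| Assumed hysteropexy share | Chance of a difference of 20 percentage points or more |
|---|---|
| 30% | about 15% |
| 50% | about 19% |

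As a cross-check, hold the total number of hysteropexies fixed and use the hypergeometric distribution. A difference of 25 points or more then has probability 9%, 12% and 15% for shares of one quarter, one third and one half (for example 9 v 3, 11 v 5 and 15 v 9).

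**3. What an imbalance does to the estimate.** Shift = difference in share × pain gap between procedures. In the trials counted in the table, the difference in share averages about 25 points. The gap is also assumed:

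| Assumed gap (NRS points) | Shift | Share of the 2.5-point target |
|---|---|---|
| 1 | 0.25 × 1 = 0.25 | 10% |
| 2 | 0.25 × 2 = 0.50 | 20% |
| 3 | 0.25 × 3 = 0.75 | 30% |

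The standard error of the difference at 21 per arm is 2.9 × √(2/21) = 0.895, so these shifts are 0.28, 0.56 and 0.84 standard errors. With procedure in the model, the average shift in the simulated trials is about zero.

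**4. What adjustment does to power.** The share of variance explained is R² = gap² × p(1 − p) / 2.9². For a gap of 2 and p = 0.5, R² = 4 × 0.25 / 8.41 = 0.119, and the residual SD falls from 2.9 to 2.9 × √0.881 = 2.72. This formula does not charge for the lost degree of freedom or for imbalance in the covariate. The table therefore uses simulation with total SD held at 2.9, 21 per arm, a true difference of 2.5 and shares of 30-50%:

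| Assumed gap | t-test, unadjusted | Linear model, adjusted |
|---|---|---|
| 0 | about 78% | about 77% |
| 1 | about 78% | about 78% |
| 2 | about 78% | 81-82% |
| 3 | about 78% | 86-88% |

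The simulated type I error is about 5% for both analyses at every gap from 0 to 3.

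**The case against.** The strongest reply is that nothing here is an error. Chance imbalance is random, the t-test's standard error already allows for it, and the test keeps its 5% level. That stands. A reader might infer bias or an inflated false-positive rate, because error conditional on a bad draw can be higher: roughly 8.6% given a 25-point imbalance and a 2-point gap, and 13.4% with a 3-point gap. Those figures describe an unlucky subset of trials under assumed gaps. Over all randomisations the level holds.

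Second, the link is diluted. Vault suspension may itself be one-sided, so planned procedure is only a proxy for number of sides. If a fraction q of vault suspensions is two-sided, the procedure effect acting through sides is q times the effect of a second side. At an assumed q of 50%, a 2-point procedure effect needs a 4-point effect of the second side, and a 3-point effect needs 6. The score is also described as a level of pain, not a sum over sides. This stands too, and it is why the gain may be small.

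Third, a reader might scale Appendix 1's 6.9 minutes by number of sides to put a figure on the device-time shift. The documents do not support that. Number of sides is a surgeon's choice that may follow allocation, and the proposed covariate would not remove imbalance in it among vault patients.

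Fourth, the sentence about procedures being uncontrolled may refer only to concomitant operations, and scheduled does not mean unchangeable. Both are fair. The point does not depend on that sentence, since the missing stratification and the unadjusted tests are stated elsewhere. The covariate should be the plan as written before allocation, whatever is done later.

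Finally, other covariates could be argued for, such as baseline pelvic pain. The documents do not rank them. Procedure is singled out because the protocol's own rules tie it to both outcomes.

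**Conclusion.** The point holds as a modest, optional improvement. The planned analysis is valid but leaves out a baseline variable that the protocol itself links to pain and device time.

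In about 15-19% of trials of this size the arms would differ by 20 points or more in hysteropexy share, shifting the pain difference by about 0.25 points per point of procedure effect. At 21 evaluable per arm, adjustment adds about 3-4 percentage points of power if the procedure effect is 2 NRS points and about 8-10 if it is 3. It adds nothing at 1 point and costs about 1 percentage point if there is no effect.

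The share (30-50%) and the effect (0-3 points) are assumptions; the documents give neither. No size is claimed for device time.

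**What to change.** In Clinical outcomes, state that NRS scores and device minutes will be compared with a linear model containing device and planned procedure (hysteropexy or vault suspension), as recorded before the envelope is opened. Keep the unadjusted t-test as a supporting analysis.

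Add one dated field for planned procedure to the preoperative inclusion form, because the baseline list in Pre-Intervention Assessments has no explicit item for it.

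Do not adjust for the actual number of sides, sutures or anchors. The surgeon may choose these after seeing the allocation, so adjusting for them could remove part of the device effect or introduce bias.

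The cost is one line of analysis text, one form field and one degree of freedom. No extra patients and no change to randomisation or surgery are needed. The wording should be settled before outcome data are examined by arm.

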To conduct a prospective, randomized, single-blind trial of sacrospinous ligament fixation of the cervix or vaginal apex using Anchorsure® system versus the CapioTM Slim device in women with \geq Stage II pelvic organ prolapse who are undergoing native tissue vaginal repair. The **primary outcome** will be the level of postoperative pain using a 10-point numerical rating scale (NRS) on postoperative day 1, week 1, and 6 weeks postoperatively for pain that is localized to the posterior thigh or buttocks on the side(s) that the sacrospinous fixation was performed. The difference in mean pain ratings will be at least 2.5 on the 10-point NRS.

Hypothesis 2: Surgeon satisfaction, surgical efficiency, intraoperative complications, objective surgical success, symptomatic success, opioid use within the first week postoperatively following hospitalization, and overall postoperative pelvic pain will be similar for both devices.

Specific Aim 2:

The **secondary outcomes** will compare overall surgeon satisfaction with the 2 devices using a 5-point Likert rating scale and surgical efficiency measured in minutes from the start of the use of the surgical device until the surgeon is satisfied with the application of all sacrospinous sutures (does not require the sutures to be tied down). Intraoperative complication related to sacrospinous ligament suspension will be recorded including the need for suture or anchor replacement, hemorrhage that requires additional surgical interventions or blood transfusion, and equipment malfunction. General postoperative pelvic pain will be assessed at postoperative day 1, week 1, and 6 weeks along with buttock and posterior thigh pain via NRS questionnaires. Objective apical repair anatomical success will be assessed at the 6 week postoperative visit via a POP-Q examination with Stage II or greater indicating anatomical failure. Symptomatic surgical success will be evaluated by statistically significant increases or decreases in the responses to the PFDI-20 and PFIQ-7 questionnaires at the 6 week postoperative values.

SUBJECT SELECTION

Inclusion Criteria

- 1. Female patients
- 2. At least 21 years of age
- 3. Surgical plan that includes a native tissue vaginal repair with apical support via sacrospinous ligament fixation. We will permit both hysteropexy and post-hysterectomy sacrospinous ligament suspension
- 4. Understanding and acceptance of the need to return for the 6 week followup visit

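### Nothing stops the unmasked surgeon from setting laterality (vault suspension) and number of sutures or anchors after seeing the allocation, and no pre-allocation plan is recorded

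*Combined protocol and SAP*

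**What the plan says.** Under Randomization and Masking, numbered sealed envelopes are used in order. The next one is "brought to the operating room where it will be opened by a participating surgeon and another operating room staff member", and both sign it. The section accepts that "it is impossible for surgeons to be masked to the randomization". Allocation is in permuted blocks of 10, with no stratification factor stated. The Calendar of Events places randomization in the intraoperative column.

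Under Study Intervention, "Surgeon discretion will determine if unilateral or bilateral fixation is performed" in vault suspension, while hysteropexy is restricted to one side. For all patients, "Surgeon discretion will determine the type and number of sutures or anchors to be placed through the sacrospinous ligament". The section says that the surgical approach and the type and number of sutures or anchors are recorded. It does not say so for laterality. The baseline list under Pre-Intervention Assessments has no item for planned laterality or planned number.

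Both outcomes depend on these choices. In Specific Aim 1, pain is scored on whichever side or sides were fixed. In Specific Aim 2, the device clock runs "until the surgeon is satisfied with the application of all sacrospinous sutures". Clinical outcomes specifies independent t-tests for pain and device time, with no covariates.

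**The concern.** The Background attributes buttock and thigh pain to nerve entrapment near the fixation, so the number and side of placements lie on the protocol's own causal path. They also feed directly into device minutes. The protocol states that better surgeon efficiency or shorter operative time would demonstrate an advantage for the anchor device, so this secondary outcome carries weight.

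The sealed, witnessed envelope protects the allocation. It does not constrain technique once the envelope is open. If surgeons tended to fix both sides, or to use more fixation points, with one of the devices, the comparison would include that difference in technique. Delivered numbers tabulated by arm might show a gap. Without a plan written beforehand, nobody could say whether the gap came from the device or from chance, or which patients were affected. That information cannot be recovered after the envelope is opened.

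**Working it through.** **1. The plan's own figure.** Power Calculation gives a difference of 2.5, SD 2.9, two-sided 5%, 80% power and 21 per group.

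n = 2 × [2.9 × (1.9600 + 0.8416) / 2.5]² = 21.12, or 22 when rounded up. Power at 21 per group is 79.8% by the normal approximation. The stated size is reproduced to within one patient per group. The standard error of the pain contrast is 2.9 × √(2/21) = 0.895.

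**2. Possible shift in the pain contrast.** Shift b = (between-arm gap in bilateral share) × (extra NRS points with bilateral fixation). The documents give neither input. Assumed ranges are a gap of 10 to 50 percentage points and 0.5 to 2 NRS points.

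With no device effect at a given technique, the two-sided rejection rate is Φ(b/0.895 − 1.96) + Φ(−b/0.895 − 1.96). If the shift works against a true 2.5-point benefit, power is computed at 2.5 − b. All rows use 21 per group.

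| Gap × increment | Shift b | Share of 2.5 | Rejection rate, no device effect | Power, true 2.5 |
|---|---|---|---|---|
| 0.10 × 0.5 | 0.05 | 2% | 5.0% | 78.2% |
| 0.30 × 1 | 0.30 | 12% | 6.3% | 69.1% |
| 0.40 × 2 | 0.80 | 32% | 14.5% | 47.6% |
| 0.50 × 2 | 1.00 | 40% | 20.1% | 38.8% |

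**3. Effect of the hysteropexy limit.** Overall gap = (share of vault cases) × (gap among vault cases). The case mix is not given. If half the cases were hysteropexy (assumed), a 40-point overall gap would need 80 points among vault cases, and a 50-point gap would need 100. The upper rows are therefore extreme unless most cases are vault suspensions. This limit does not apply to the number of sutures or anchors, which is discretionary in every patient.

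**4. Chance imbalance.** With a bilateral share p in both arms, the SD of the between-arm difference is √(2p(1 − p)/21): 14 points at p = 0.3 and 15 points at p = 0.5. An observed gap of that order needs no surgeon influence. The t-test's standard error already allows for this chance component, so it costs precision rather than validity. It also means that a table of delivered technique alone could not separate chance from device-driven choice.

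**5. Device time.** Appendix 1 gives 6.9 minutes for fixation alone with the suture-capture device and does not say whether that is one side. Assume that it is, that bilateral fixation doubles it, and that 30% to 50% of cases are bilateral. The variance due to laterality is 6.9² × p(1 − p):

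- p = 0.3: 47.61 × 0.21 = 10.0, SD 3.2 min
- p = 0.5: 47.61 × 0.25 = 11.9, SD 3.5 min

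If the SD within laterality is 2 to 4 minutes (also assumed), the share of total variance runs from 10.0/(10.0 + 16) = 38% to 11.9/(11.9 + 4) = 75%.

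**The case against.** A reader might infer that the device effect is confounded. The documents do not support that word. A choice made in response to the assigned device is a post-randomisation co-intervention, and the randomised comparison still validly estimates the device as these experienced surgeons use it. Leaving technique to discretion looks deliberate.

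A reader might also infer that surgeons make these choices after seeing the allocation. The protocol does not say when the envelope is opened relative to them; it only fails to prevent it. Nor is laterality open for every patient, since hysteropexy is fixed at one side.

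The remedy has a limit. Planned laterality is balanced by randomisation in expectation, so adjusting for it does not remove switching, and the shifts in the table are not what the covariate would recover. Adjusting for delivered technique would condition on a post-randomisation choice. Number is partly intrinsic to the device, so a count that applies to both devices needs a definition.

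Existing protections count too: sealed, witnessed envelopes, participants masked as far as possible, a patient-reported primary outcome, a common placement limit for both devices, and recording of suture or anchor type and number.

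All of this stands. None of it supplies a plan recorded before allocation, and none of it equalises technique between arms.

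**Conclusion.** The gap is real, and it is one of documentation and analysis. The plan does not prevent laterality (in vault suspension) or number (in all patients) from being chosen in the light of the allocation. It also keeps no record from which such choices could be recognised.

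For pain, the shift is 0.05 to 1.0 NRS points on wholly assumed inputs. It may be negligible, and the upper end needs a very uneven use of bilateral fixation. For device time the dependence is direct by definition of the endpoint, but its size (SD about 3.2 to 3.5 minutes from laterality) again rests on assumptions about what 6.9 minutes represents, doubling, and the bilateral share. It would be too strong to say that the plan is known to carry large avoidable variance.

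The point does not undermine the trial. The change is worth making because it is cheap and cannot be made retrospectively.

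**What to change.** **Randomization and Masking.** Before the envelope is opened, the surgeon writes the planned laterality and planned number of fixation points on the envelope or on an attached sheet. Define a fixation point once so that it can be counted for either device. The surgeon remains free to depart from the plan.

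**Clinical outcomes.** Replace the unadjusted t-tests for pain and device time with linear models containing device, planned laterality and planned procedure (hysteropexy or vault suspension). Because hysteropexy is always unilateral, the two covariates define three groups and cost two degrees of freedom (42 − 2 = 40 becomes 38 with 21 per group). State explicitly that delivered laterality is recorded, and report actual against planned laterality and number by arm.

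State also that the covariates correct chance imbalance and improve precision but do not remove device-driven switching, which the actual-against-planned table only makes visible.

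**Cost.** Two written fields, two covariates and one table. The small downside is that surgeons must put a plan on record.
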